We hypothesize that noninvasive tDCS in conjunction with TUS can be effective in decreasing the perception of pain in subjects with OA of the knee. To test this, we will use sensitive, currently validated outcomes for chronic pain subjects. A rater blind to the treatment arm will administer the following tests: Visual Analog Score (VAS) for Pain, Pain/Medication Diary, Von Frey assessment, and pain pressure tests (PPT) with algometer following stimulation detailed above, in SubAim 1.1. We will compare the stimulation conditions as above. Follow-up evaluations will continue, while no further treatment is given, for 8 weeks (at 1, 2, 4, and 8 weeks) after the last stimulation.

Sub Aim 1.3 Effects of tDCS+TUS in biomechanical function in subjects with OA of the knee.

We hypothesize that tDCS in conjunction with TUS can be effective in improving the biomechanical function in subjects with OA of the knee. To test this, we will compare the impact of active tDCS in conjunction with active TUS to the other stimulation conditions, as above, on markers of biomechanical function. We will use a biomechanical data acquisition and analysis system to specifically assess subject's knee biomechanical functionality and response to the intervention. For this purpose we will use a set of integrated sensors including accelerometers, gyroscopes, force sensors, and motion-capture cameras. Follow-up evaluations will continue, while no further treatment is given, for 8 weeks (at 1, 2, 4, and 8 weeks) after the last stimulation.

Sub Aim 1.4. Effects of tDCS+TUS in the quality of life in subjects with OA of the knee.

We hypothesize that tDCS in conjunction with TUS can be effective in improving the quality of life (QOL) in subjects with OA of the knee. To examine this aim, we will implement the Western Ontario and McMaster Universities Osteoarthritis Index (WOMAC), as this is recommended as one of the most sensitive and specific instruments for quality of life assessment in OA [68] and physical functioning assessment including a wide range of daily activities, such as bathing and getting in or out of the car. We will also use a generic health status measure - the Medical Outcomes Study 36-Item Short Form (SF-36) [68]. We will compare the stimulation conditions as above. Follow-up evaluations will continue, while no further treatment is given, for 8 weeks (at 1, 2, 4, and 8 weeks) after the last stimulation.

IV. SUBJECT SELECTION

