We will recruit up to 94 subjects for this study, with the intention of randomizing exactly 64 subjects with OA of the knee for this study. Once we randomize 64 subjects, we will stop recruiting subjects. Subjects will need to meet all of the following inclusion criteria and none of the following exclusion criteria:

Inclusion Criteria:

1. Able to provide informed consent to participate in the study.
2. Subjects between 18-85 years old.
3. Diagnosis of chronic osteoarthritis with pain of either knee as self-reported. *Prior to beginning baseline procedures this must be confirmed by medical records or a letter from the subject's physician, or diagnosis by a study staff licensed physician. This document may either be brought in by the subject or retrieved by study staff after the subject signs a medical release form. If the subject is unable to obtain the medical record, a diagnosis by a study staff licensed physician will be accepted. After consent, if the subject fails to provide the necessary documentation, or if it cannot be retrieved by study staff, the subject will be considered a screen fail.*
4. Existing knee pain of at least 3 on a 0-10 VAS scale on average over the past 6 months.
5. Pain of at least 3 on a 0-10 VAS scale on average over the week prior to the first stimulation session.
6. Pain resistant to common analgesics and medications for chronic pain used as initial pain management such as Tylenol, Aspirin, Ibuprofen, Soma, Parafon Forte DCS, Zanaflex, and Codeine.
7. Having the ability to feel pain as self-reported.

Exclusion Criteria:

1. Pregnancy or trying to become pregnant in the next 6 months.
2. History of alcohol or drug abuse within the past 6 months as self-reported.
3. Contraindications to transcranial brain stimulation or TUS, e.g. implanted brain medical devices or implanted brain metallic devices.
4. Unstable medical conditions (e.g. uncontrolled diabetes, uncompensated cardiac issues, heart failure or chronic obstructive pulmonary disease).
5. Epilepsy.
6. Use of carbamazepine within the past 6 months as self-reported.
7. Suffering from severe depression (with a score of >30 in the Beck Depression Inventory).
8. History of unexplained fainting spells as self-reported.

9. Head injury resulting in more than a momentary loss of consciousness.
10. History of neurosurgery as self-reported.

V. SUBJECT ENROLLMENT

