An FDA approved assist device (Highland Instruments, Cambridge, MA) that can assist the stimulation provider in the synchronous application of TUS

and cranial electrical stimulation devices will be available if required (e.g., for operator fatigue the device can assist the operator in holding the TUS probe relative to the tDCS electrodes).

For sham tDCS/TUS, we will follow the exact procedure as above but use an inactive ultrasound transducer (i.e., the device will remain off during stimulation). For the sham condition, we will follow the exact procedure as above, however tDCS current will be applied for less than 30 seconds so that the sham subjects experience the same sensation of the device turning on as active subjects (the 'turning off' of the device is not perceived due to sensitization). It should be noted that less than 3 minutes of tDCS induces no lasting effects on cortical excitability [39]) and also using 30 seconds of sham is a reliable method of blinding, as shown by a randomized controlled study [69].

[REDACTED] Furthermore during the sham, the TUS will not be active during stimulation.

The schedule for the subjects can be seen in table 1, which illustrates the procedures that will be performed at each visit:

[REDACTED]

[REDACTED]

DESCRIPTION OF ASSESSMENTS:

A rater blind to the treatment arm will administer the following tests (also used in our previous study [70]):

Visual Analogue Scale (VAS) for Pain: The VAS is a common assessment used which asks subjects to self-reportedly measure their pain on a visual scale (i.e., unbearable to none). This will help us to monitor changes in subjects' pain levels when they come in for sessions.

Pain/Medication Diary: To help monitor pain levels, as well as safety, subjects will keep a diary listing their daily medications and pain levels when not at the laboratory.

Mechanical Detection Threshold (von-Frey MDT): This technique is adapted to evaluate light touch in small cutaneous regions [71]. The most used procedure is with the Von Frey monofilament (0.008g to 300g) via the method of limits. The examiner makes use of an ascending standardized sequence of varying stimulus intensities. In the case of ramping the stimulus up, the individual is asked to report when the sensation is first detected

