Single applications of standardized monofilaments will be applied first to a reference region (thenar region, ipsilateral to the most painful knee), using the smallest weighted monofilament, followed by sequentially larger monofilaments until sensation is reported [71]. Following the reference region, the most painful knee will be tested. The monofilaments must be applied perpendicular to the skin and bow for a period of approximately 1.5 seconds [71, 72]. The threshold will be taken as the lowest force that causes a light touch sensation

Mechanical Pain Thresholds (von-Frey MPT): The evaluation of mechanical pain thresholds is performed using standardized, fine, blunt-tipped probes. The threshold to produce pain is recorded in this test. The force applied by the Von Frey monofilament is standardized by applying just the right amount of force to bow the monofilament for approximately 1.5 seconds [71, 72]. The subjects will be asked to say when they sense pain. The thenar region, ipsilateral to the most painful knee will be tested. Following the reference region, the most painful knee will be tested. The smallest monofilament that produces pain will be recorded.

Fixed Intensity hyperalgesia evaluation (von-Frey hyperalgesia): To study hyperalgesia the previously registered smallest monofilament to produce pain in the thenar region will be used [71]. A standard stimulus of fixed intensity will be applied over the thenar region, ipsilateral to the most painful knee, and the subject will be asked to rate the sensation of pain using a visual analogue scale for pain. The process will be done 3 times and the geometric mean of the visual analogous scale will be calculated. Following the procedure, the most painful knee will be studied and the subject will be asked to rate the sensation of pain using a visual analogous scale for pain. The process will be done 3 times and the geometric mean of the visual analogous scale will be calculated.

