All analyses will be conducted according to the principle of intention-to-treat (using regression-based single imputation method). Intention-to-treat (ITT) population will include all randomized subjects. We will also perform an additional sensitivity analysis in which we will use the method of multiple imputation. The primary outcomes will be pain changes as indexed by VAS scores, biomechanical function changes as indexed with the motion analysis suite (i.e., our biomechanical data acquisition and analysis system), and QOL changes. Differences between the groups will be tested using Student's t-test, and additionally we will adjust for important baseline variables and test the time effect in general mixed longitudinal models. This model will be used for the primary and secondary outcomes (dependent variable (one model for each variable): VAS scores, biomechanical function changes as indexed with the motion analysis suite, and QOL changes, and independent variables will be treatment group and time of assessment (we will also adjust for baseline pain levels in this model)). Secondary analyses will be conducted in an exploratory manner (no correction for multiple comparisons). We will also conduct an EEG analysis to correlate EEG data with pain measures. Similar analysis will be conducted for the adverse effects measuring continuous outcome and for the categorical outcomes we will use Fisher's exact test. In both cases, for safety analysis we will use uncorrected p-value to increase the likelihood of detecting detrimental adverse effects.

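### The von Frey hyperalgesia score is a geometric mean of three pain ratings that may include zero, with no rule for zeros, so one zero makes the score 0 or undefined; the measure is not a primary outcome

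*Combined protocol and SAP*

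**What the plan says.** The rule is in Section VI, Description of Assessments, under Fixed Intensity hyperalgesia evaluation. On the stimulus: "To study hyperalgesia the previously registered smallest monofilament to produce pain in the thenar region will be used". On the response: "the subject will be asked to rate the sensation of pain using a visual analogue scale for pain". On the summary: "The process will be done 3 times and the geometric mean of the visual analogous scale will be calculated". The summary sentence appears twice, once for the thenar region and once for the most painful knee.

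Two other places fix the scale. The description of the VAS for Pain says that subjects "measure their pain on a visual scale (i.e., unbearable to none", so the lower end means no pain. Section IV uses the scale numerically: "Existing knee pain of at least 3 on a 0-10 VAS scale on average over the past 6 months". No separate range is given for the von Frey ratings.

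On the role of the measure, Sub Aim 1.2 in Section II lists the von Frey assessment among the pain-perception tests: "Pain/Medication Diary, Von Frey assessment, and pain pressure tests (PPT) with algometer following stimulation detailed above, in SubAim 1.1". Section VII does not list it as primary: "The primary outcomes will be pain changes as indexed by VAS scores, biomechanical function changes as indexed with the motion analysis suite", together with quality of life. That section calls secondary analyses exploratory and does not correct them for multiplicity.

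The documents contain no offset, floor value or alternative summary for a zero rating.

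**The concern.** A geometric mean suits strictly positive quantities that vary by ratios. A pain rating with a true zero is not one of these. A single zero overrides the other two ratings, so the score can rank a patient with clear pain below one with slight pain. If the calculation goes through logarithms, the same patient has no score at all. The protocol does not say which applies, so two programmers could produce different data from the same ratings.

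Zeros are foreseeable. The filament is the smallest that produced pain at the thenar, so repeats at that site are given at threshold and some may not hurt.

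What is at stake is the ordering of patients and the precision of one pain-perception measure. The visit schedule lists the von Frey assessment at baseline, before and after the first stimulation, on stimulation days 5 and 10, and at four follow-ups: 1 + 2 + 2 + 4 = 9 occasions, with two sites each.

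**Working it through.** The documents give no figure for this score, so there is none to reproduce. The inputs taken from them are three ratings per site, a 0-10 scale, 32 patients per arm and Student's t-test. Latent means, SDs and zero probabilities are assumptions, as is the two-sided 0.05 level.

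**1. Single scores.** The geometric mean is GM = (x1·x2·x3)^(1/3).

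| Ratings | Geometric mean | Arithmetic mean |
|---|---|---|
| 9, 9, 0 | 0 | 6.0 |
| 3, 3, 0 | 0 | 2.0 |
| 0, 0, 0 | 0 | 0 |
| 1, 1, 1 | 1 | 1 |
| 3, 3, 0.1 | 0.97 | 2.03 |
| 4, 5, 6 | 4.93 | 5.0 |

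The first three patients are indistinguishable, and all rank below the fourth. With no rating at or near zero, the two summaries almost agree.

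**2. How often a score becomes 0.** If each rating is independently zero with probability p, P(score = 0) = 1 − (1 − p)^3, while all three ratings are zero with probability p^3.

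| p (assumed) | Score 0 | All three ratings 0 |
|---|---|---|
| 0.01 | 3.0% | under 0.01% |
| 0.05 | 14.3% | 0.01% |
| 0.10 | 27.1% | 0.1% |
| 0.20 | 48.8% | 0.8% |
| 0.50 | 87.5% | 12.5% |

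Independence overstates the first column if zeros cluster within patients.

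**3. Power.** Three ratings per patient were simulated as normal latent values, cut at 0 and 10 and rounded to 0.1. There were 32 patients per arm, a latent difference of 0.8 and a between-person SD of 0.8. With 2,000 to 4,000 trials per scenario, the Monte Carlo standard error is about 1 percentage point or less.

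| Latent means | Within-test SD | Arithmetic | Geometric | Loss (points) |
|---|---|---|---|---|
| 4.0 v 3.2 | 0.7 | 95% | 95% | 0 |
| 4.0 v 3.2 | 1.5 | 77% | 72% | 5 |
| 2.0 v 1.2 | 0.7 | 94% | 93% | 1 |
| 2.0 v 1.2 | 1.0 | 88% | 84% | 4 |
| 2.0 v 1.2 | 1.5 | 74% | 63-64% | 10-11 |

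A second set used a 1-point difference with both SDs at 1.0. It gave losses of 92.9 − 92.5 = 0.4 points (means 5 v 4), 92.5 − 91.6 = 0.9 (3 v 2) and 91.1 − 87.7 = 3.4 (2 v 1). The loss comes from extra spread, not from a smaller difference. At mean 2 the SD is 1.23 for the geometric and 1.07 for the arithmetic score. In the worst row of the table the mean difference is 0.71 geometric and 0.66 arithmetic.

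**4. Type I error.** With equal latent means and both SDs at 1.0 in both arms, the geometric score rejects in 4.9% to 5.3% of trials. With latent mean 2.5 and between-person SD 0.8 in both arms, but within-test SD 0.7 in one arm and 1.6 in the other, the mean geometric score is 2.41 v 2.03 and the t-test rejects in 23% of trials. The arithmetic means are 2.50 v 2.57, with 6% rejection.

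**5. If zeros become missing through logs.** With means 2.0 v 1.2 and within-test SD 1.5, about 30% v 53% of scores are lost. The complete-case difference is 0.44, against 0.66 for arithmetic means of all patients.

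**The case against.** The strongest reply is that little depends on this score. It is one of three von Frey sub-measures, it is not primary, and Section VII never names it. No sample-size or safety decision rests on it. This stands, and it limits the grade of the point.

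A reader might infer that the rule distorts the comparison of arms and visits in general. The documents do not support that. Both randomised arms are scored by the same rule, and type I error stays near 5% when variability within a test is equal. The inflated rejection rate needs one arm to be much more erratic at the same mean pain, and nothing in the documents suggests that stimulation does this.

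A reader might also infer that a large share of scores will be zero. The threshold stimulus makes zeros plausible, but no frequency is given. The patient has already reported that filament as painful at the thenar, and at a sensitised knee the same filament could rate well above zero.

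The loss of scores through logs is conditional too, since the documents do not say that logs are used. Nor would it remove only the patients with the least hyperalgesia: ratings of 0, 4 and 5 would be lost as well.

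Finally, the protocol cites a source for the procedure and says that the tests were used in an earlier study. A zero convention may exist there. It cannot be confirmed from these documents, and the protocol does not carry one over.

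**Conclusion.** The point holds as a defect in a stated scoring rule, not merely a missing detail: followed as written, the rule ranks 9, 9, 0 below 1, 1, 1. That is arithmetic and needs no assumption beyond zero being an allowed rating.

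The consequence is modest and uncertain. It depends on how often ratings fall at or near zero, which the documents do not give. In the scenarios tried with equal variability in the arms, the cost runs from nothing to about 11 points of power, and the upper end needs both low ratings and large variation between repeats. It is worth correcting before analysis because the measure serves Sub Aim 1.2 and the correction is easy.

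**What to change.** In both sentences of the hyperalgesia paragraph, for the thenar and for the knee, replace the geometric mean with the arithmetic mean of the three ratings. It is defined at zero and barely changes scores that contain no low rating. Where only the geometric mean was stored, recompute from the source ratings.

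If the geometric mean is wanted for comparability with the earlier study, report it as a sensitivity score with a fixed, prespecified offset added before averaging. With an offset of 1, subtracted again afterwards, 9, 9, 0 gives (10·10·1)^(1/3) − 1 = 3.64 and 3, 3, 0 gives (4·4·1)^(1/3) − 1 = 1.52, so patients with one zero are again told apart.

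The cost is one word in each of two sentences and, where needed, a recalculation. No additional measurement is required. The one small downside is that the new scores are not directly comparable with any earlier geometric-mean scores.

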Pain pressure tests (PPT): PPT will be determined using blunt pressure delivered by a 1-cm² hard-rubber probe using a FDA approved device (commander algometer – JTECH medical). During testing a series of discrete pressures are applied to a reference area, the thenar area ipsilateral to the most painful knee. Following the reference region testing, the most painful knee will be tested. The subject will let the investigator know when he/she feels any pain, and at that time the procedure will be stopped, and the value will be recorded. This procedure will be repeated 3 times. The test will take approximately 7-10 min to complete.

Descending Noxious Inhibitory Control (DNIC): Endogenous pain modulation is commonly evaluated in the laboratory using DNIC testing paradigms. These procedures incorporate a conditioning stimulus (a noxious stimulus that evokes DNIC activation) and a test stimulus (a noxious stimulus used to evaluate the analgesic response to the conditioning stimulus - this will be the PPT). This study will evaluate DNIC in pain patients using pressure as the test stimulus, and cold water as the conditioning stimulus. Pressure will be delivered using the same device as for the evaluation of PPT. DNIC will be induced approximately 1-min later by having subjects immerse their hand into a water bath maintained at 10-12°C for approximately 1 min. Parallel to the last 30s of DNIC conditioning (cold water immersion), the same test stimulus will be reapplied (PPT procedure). DNIC will be evaluated as the mean difference in pain rating of the test stimulus applied before and during the conditioning stimulus. This value would typically be treated as a continuous variable if measured repeatedly in a clinical trial because it is unlikely that descending analgesic systems are either “on” or “off”, but rather function within a range of magnitudes across subjects.

EEG recording: One week prior to stimulation, on the first day of stimulation, at the end of each stimulation week, and during each follow up visit, EEG recordings will be taken to monitor brain activity and saved for post recording evaluation.

Neurological and Physical Exam: Trained study staff will conduct baseline and follow-up neurological examinations focused to ensure subject safety one week prior to stimulation, on the first day of stimulation, at the end of each stimulation week, and during each follow up visit [73].

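### DNIC is scored as a change in pain rating, but its test stimulus (the PPT) records a pressure value, and the readings to take during immersion are not stated

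*Combined protocol and SAP*

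**What the plan says.** The relevant text is in the combined protocol and SAP, Section VI, under the description of assessments.

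- **DNIC, score:** "DNIC will be evaluated as the mean difference in pain rating of the test stimulus applied before and during the conditioning stimulus". The order of subtraction is not given.
- **DNIC, test stimulus:** "a noxious stimulus used to evaluate the analgesic response to the conditioning stimulus - this will be the PPT".
- **DNIC, conditioning and timing:** the conditioning stimulus is cold water, applied by "having subjects immerse their hand into a water bath maintained at" a stated temperature for about one minute. The text continues: "Parallel to the last 30s of DNIC conditioning (cold water immersion), the same test stimulus will be reapplied (PPT procedure").
- **PPT:** pressure is applied in steps, first to the thenar area on the side of the most painful knee and then to that knee. The subject reports when he or she "feels any pain, and at that time the procedure will be stopped, and the value will be recorded". Then: "This procedure will be repeated 3 times". And: "The test will take approximately 7-10 min to complete".
- **Von Frey fixed-intensity hyperalgesia test, for comparison:** a stimulus of set strength is applied and "the subject will be asked to rate the sensation of pain using a visual analogue scale for pain".

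The visit lists in Section VI schedule DNIC at baseline, before and after the first stimulation, at visits 7 and 12, and at the four follow-up visits. Section VII names the primary outcomes as VAS pain, biomechanical function and quality of life. It does not mention DNIC, and neither does the list of tests under Sub Aim 1.2.

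**The concern.** A score has to be computable from what the procedure records. Here the procedure yields a pressure, and the scoring sentence asks for a difference between ratings. The two also run in opposite directions: stronger inhibition raises a pressure threshold but lowers a pain rating. If the choice is left open, scores obtained in different ways cannot be pooled, and the sign of a result is ambiguous. Fixing the quantity after data are in hand would also add freedom to an exploratory analysis.

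The second gap concerns the 30 s window. The PPT has two sites and repeats, and the DNIC paragraph does not say which of these readings are taken during immersion. It also does not say which hand is immersed, although one PPT site lies on a hand.

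Participants undergo the test at 1 + 2 + 1 + 1 + 4 = 9 time points, so up to 9 × 64 = 576 cold-water immersions are at stake.

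**Working it through.** **1. Quantity recorded against quantity scored**

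| Element | PPT | Von Frey hyperalgesia | DNIC scoring sentence |
|---|---|---|---|
| Stimulus | Steps of pressure up to first pain | Fixed intensity | The PPT |
| Rating step | None | Pain VAS | Rating assumed, step not described |
| Output | Pressure value | VAS score | Difference in rating |

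The plan writes out the stimulus and the scale where it wants a rating. For DNIC it gives neither.

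**2. Would adding a rating repair the rule?** Assumed values, for illustration only: threshold 4.0 before and 5.0 during immersion (arbitrary units), first pain rated 1 out of 10.

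- Pressure difference: 5.0 − 4.0 = +1.0, which shows inhibition.
- Rating at the stopping point: 1 − 1 = 0. The PPT stops at first pain both times by design, so the shift is invisible.
- Rating of a fixed pressure of 4.0 applied again: 0 − 1 = −1, which shows inhibition with the opposite sign.

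Only the first and third carry the information. The third needs a fixed pressure, and is then no longer the PPT procedure.

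**3. Time.** Inputs from the PPT and DNIC paragraphs: full test 7 to 10 min = 420 to 600 s; window 30 s; immersion about 60 s. The plan gives no time for a single reading. The last three rows therefore assume that the total is shared equally over 2 sites × 3 readings = 6 readings.

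| Portion of the PPT | Time | Ratio to 30 s |
|---|---|---|
| Full test | 420 to 600 s | 14 to 20 |
| One site, three readings (÷2) | 210 to 300 s | 7 to 10 |
| Both sites once (÷3) | 140 to 200 s | 4.7 to 6.7 |
| One reading (÷6) | 70 to 100 s | 2.3 to 3.3 |

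The full test also exceeds the whole immersion, by 420/60 = 7 to 600/60 = 10 times. One reading would fit in 30 s if set-up and rest made up at least 1 − 30/70 = 57% (7 min) to 1 − 30/100 = 70% (10 min) of the stated time. That is possible, and the documents do not settle it.

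**4. Site and hand.** The DNIC paragraph names neither a PPT site nor the hand to be immersed. The knee is a PPT site away from either hand.

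**The case against.** **A single run may be meant.** In the PPT paragraph, what is stopped at first pain and then repeated is most naturally one run, while the 7 to 10 minutes belong to the test as a whole. DNIC reapplies the stimulus and refers to the PPT procedure. On that reading the ratio of 14 to 20 compares a whole session with one application. This stands. A reader might infer from the ratio that DNIC cannot be done in 30 s at all, but the documents do not support that. They support only that the full test does not fit, and that the site and number of readings are unstated.

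**A rating may be what the sponsor intended.** The DNIC paragraph also speaks of pressure as the test stimulus, delivered with the same device as the PPT, and the trial already uses a pain VAS. This is a fair reading of intent, so the rating route has to remain open. It does not remove the contradiction: the paragraph names the PPT as the stimulus, and gives no fixed pressure and no scale.

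**Staff may already have a settled method.** The section says the tests were used in the group's previous study. That may be so, and it cannot be checked here. A reader should not infer that staff are improvising, but this plan still has to state the rule it will apply.

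**The measure is secondary at most.** Agreed. A reader might infer bias towards one arm or a threat to the trial's main result. Neither is supported: assessments are made by a rater blind to arm, DNIC is not a primary outcome, and secondary analyses are declared exploratory.

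**Conclusion.** The point holds and is minor. The DNIC scoring rule contradicts the procedure it relies on: the PPT gives a pressure, the score calls for a rating, and a rating taken at the PPT's stopping point would give a difference near zero by design. This follows from the text alone. The worked values above only illustrate it.

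The timing part is narrower. The full PPT cannot be repeated in 30 s, and the plan does not say which part is. Whether a single reading fits depends on an unstated time per reading.

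The consequence is limited to DNIC: noisy, unpoolable or ambiguously signed scores at up to nine time points per participant. The documents give no DNIC variance or effect, so the loss cannot be put as a power figure.

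**What to change.** Reconcile the DNIC and PPT paragraphs in one of two ways.

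**If a threshold is meant:**

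- Replace the rating with the PPT pressure value. Define DNIC as the value during immersion minus the value before it at the same site, so that a positive score means inhibition.
- Name one site away from the immersed hand; the most painful knee is an existing PPT site. Name the hand, and use the same one at every visit.
- Keep the usual repeats before immersion, since only the second measurement faces the 30 s limit. State how many readings are taken in the window, after timing a few single readings.
- If a reading is unfinished when the window closes, record the highest pressure reached without pain as a lower bound (a censored value). Setting it to missing would tend to drop the highest thresholds, hence the strongest inhibition, and Section VII would then fill the gap by regression imputation. State how the analysis handles lower bounds, because a t-test on the raw values does not.

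**If a rating is meant:** state a fixed test pressure and a rating scale, and stop calling the step the PPT procedure.

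**Cost:** a few sentences, one or two fields on the data form, and the scoring program; no new equipment or visits. The score may not match the group's earlier scoring.

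Fewer readings during immersion also add some noise. With independent readings of error variance s², three before and one during give s²/3 + s² = 4s²/3. Three and three would give 2s²/3, so the error variance doubles. One and one would give 2s², three times as much, which is why the repeats before immersion are worth keeping. Let R be the reliability of a one-and-one difference (assumed). The total SD with three and one, relative to three and three, is √[(R + 2(1−R)/3) / (R + (1−R)/3)]. That is 1.04, 1.09 and 1.15 for R = 0.8, 0.6 and 0.4. These figures price the fix, not the defect.
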